### 9.7.4 Analysis of secondary objectives

With regard to objective #3, similarly as in the analysis of the primary objectives, the prevalence of the pregnancy outcomes (i.e. serious adverse pregnancy outcome, elective TOPFA, stillbirth, live birth and MCA) will be compared between the study cohorts specified in Section 8.

With regard to objective #4, the descriptive statistics including number (n) and prevalence (%) of ectopic pregnancies and spontaneous abortions will be presented in each study cohort separately. The prevalence of these pregnancy outcomes will be compared between the study cohorts specified in Section 8.

With regard to objective #5, the descriptive statistics (n and %) of the pregnancy outcomes (i.e. serious adverse pregnancy outcome, elective TOPFA, stillbirth, live birth and MCA) will be further described for study cohorts 1 – 4 stratified by country, year of pregnancy outcome, maternal age at LMP, any chronic diseases, exposure to any teratogenic medications including steroids, time since MS diagnosis, duration of MS treatment, gestational age and weight of the newborn as relevant for specific pregnancy outcomes and as the number of events allow.

### 9.7.5 Analysis of exploratory objectives

With regard to objective #6, only live births will be included in the analyses on birth health. The descriptive statistics given in Table 7 are to be presented for each additional pregnancy outcome in each study cohort 1 – 4 separately.

**Table 7: Descriptive statistics calculation for each additional pregnancy outcome.**

Pregnancy outcome	Descriptive statistics
Mode of delivery (CS/vaginal)	number (n), prevalence (%)
Preterm birth	number (n), prevalence (%)
Birth weight	mean, median, SD, minimum, maximum and inter-quartile range
LBW	number (n), prevalence (%)
Birth height	mean, median, SD, minimum, maximum and inter-quartile range
LBH	number (n), prevalence (%)
Weight adjusted for gestational age (SGA, AGA, LGA)	number (n), prevalence (%)
Sex of the newborn	number (n), prevalence (%)
Head circumference	mean, median, SD, minimum, maximum and inter-quartile range
Low head circumference	number of events (n), prevalence (%)
Apgar score (at 1 and 5 minutes)	mean, median, SD, minimum, maximum and inter-quartile range
Defect cases	number (n), prevalence (%)

With regard to objective #7, the pregnancy outcomes (n, %) of i) congenital malformations in live or still births, ii) ectopic pregnancies, iii) spontaneous abortions, and iv) live births in the general population without MS diagnosis in FIN, SWE and NOR (cohort 6) are to be estimated based on relevant official birth health statistics available from these countries. This is to be done by subtracting the prevalence attributable to MS-diagnosed women from the prevalence in the general population and dividing this by the proportion of pregnancies without an MS diagnosis. Thereafter, the observed numbers of pregnancy outcomes matched for age and country in cohort 3 will be compared to the numbers calculated for cohort 6. In these comparisons, the standardised prevalence ratio (ratio of the expected and observed prevalent cases) with 95% CI will be used.

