  - iii) women with MS exposed to IFN- $\beta$  regardless of exposure to other MSDMDs (cohort 2) vs. unexposed to any MSDMDs (cohort 3).This objective is subject to available data from each country, as only information on ectopic pregnancies or spontaneous abortions requiring treatment in hospitals is available in the study.
5. To estimate the prevalence of the pregnancy outcomes (i.e. serious adverse pregnancy outcome, elective TOPFA (not possible in SWE), stillbirth, live birth and MCA) in cohorts 1 – 4 stratified by country, year of pregnancy outcome, maternal age at LMP, chronic diseases, exposure to any teratogenic medications including steroids, time since MS diagnosis, duration of MS treatment, gestational age and weight of the newborn as relevant for specific pregnancy outcomes.

**The exploratory objectives** are:

6. To describe the following additional characteristics about pregnancy in cohorts 1 – 4:
  - Mode of delivery (CS/vaginal)
  - Preterm birth
  - Birth weight and LBW
  - Birth height and low birth height (LBH), according to country specific standards (FIN Sankilampi et al. 2013)
  - Birth weight (SGA and LGA), height and head circumference for gestational age (AGA)
  - Sex of the newborn
  - Head circumference and low head circumference (according to country-specific standards (FIN Sankilampi et al. 2013)
  - Apgar score (at 1 and 5 minutes)
  - Defect cases
  
7. To estimate the prevalence of i) congenital malformations in live or stillbirths, ii) ectopic pregnancies, iii) spontaneous abortions, and iv) stillbirths in the general population without MS diagnosis (cohort 6) in FIN, SWE, NOR for each pregnancy outcome separately as available in each country. The observed numbers of pregnancy outcomes in cohort 3, matched for age and country, are compared with the expected numbers through indirect standardisation under the assumption that cohort 3 had experienced the same prevalence as women in the general population without MS diagnosis (cohort 6).

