### **Register on Induced Abortions (FIN)**

In the Nordic countries, statistics on induced abortions are based on case data on an individual level (Gissler 2010). In SWE, however, the data collection is anonymous, and in NOR, the data collection is anonymous before 12 weeks of gestation. In FIN there is a separate Register on Induced Abortions and Sterilisations.

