### Elective terminations of pregnancy

Information on TOPFA and abortions due to other reasons will be obtained from the DPP (FIN) and MBR (NOR). The Finnish Abortion Register, which is the data source for the DPP regarding pregnancy terminations, collects data on all terminations performed in FIN since 1977. The national abortion legislation requires permission with a legal indication for terminating a pregnancy. The data of the Abortion Register are obtained from hospitals and Valvira. The information is completed with information from the national Hospital Discharge Register. More than 99% of all elective TOPs (regardless of reason of the termination (maternal social or health related, foetal related health) registered in hospital records are included in the Abortion Register (Gissler et al. 1995, Gissler et al. 1996). In NOR, abortions are included in the MBR from 12 GW onwards. SWE does not have a register on abortions.

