### 9.7.2 Denominators used for different pregnancy outcomes

The denominator used for the calculation of the descriptive statistics and prevalence of specific pregnancy outcomes in each study cohort varies by pregnancy outcome. Table 6 below describes how the denominators are defined for each pregnancy outcome.

**Table 6: Denominators used for calculation of the descriptive statistics and prevalence of pregnancy outcomes in each study cohort.**

Pregnancy outcome	Denominator used in each study cohort
Serious adverse pregnancy outcome	Number of elective terminations + number of births (still or live)
Elective TOPFA or other reasons	Number of elective terminations + number of births (still or live)
Still births	Number of elective terminations + number of births (still or live)
Live births	Number of elective terminations + number of births (still or live)
MCA	Number of elective terminations + number of births (still or live)
MCA in live births	Number of live births
Mode of delivery (CS/vaginal)	Number of live births, separately for single and multiple pregnancies
Preterm birth	Number of live births, separately for single and multiple pregnancies
Birth weight, LBW and birth weight, head circumference for gestational age	Number of live births, separately for single and multiple pregnancies
Sex of the newborn	Number of live births, separately for single and multiple pregnancies
Head circumference, low head circumference	Number of full-term live births, separately for single and multiple pregnancies
Apgar scores	Number of full-term live births, separately for single and multiple pregnancies
Ectopic pregnancies	Number of all pregnancy events
Spontaneous abortions	Number of all pregnancy events
Defect cases	Number of elective terminations + number of births (still or live)

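### Objective 7: the Table 6 denominators count terminations that cohort 3 cannot see in Sweden or early Norwegian pregnancy but national statistics can, so the standardised ratios can depart from 1 with no true difference

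*Protocol*

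**What the plan says.** - **Benchmark.** Section 9.7.5 states that the cohort 6 outcomes "are to be estimated based on relevant official birth health statistics available from these countries". In Section 8, objective 7, the cohort 3 counts "are compared with the expected numbers through indirect standardisation", by age and country. Section 9.7.5 adds that "the standardised prevalence ratio (ratio of the expected and observed prevalent cases) with 95% CI will be used".
- **Denominators.** Table 6 (Section 9.7.2) is titled "Denominators used for calculation of the descriptive statistics and prevalence of pregnancy outcomes in each study cohort", and Section 8 lists cohort 6 among the study cohorts. For live birth and stillbirth the denominator is "Number of elective terminations + number of births (still or live"). For spontaneous abortion and ectopic pregnancy it is "Number of all pregnancy events", and Section 9.7.1 counts terminations as pregnancy events.
- **What each side can see.** On induced-abortion statistics, Section 9.3.1.2 says: "In SWE, however, the data collection is anonymous, and in NOR, the data collection is anonymous before 12 weeks of gestation". Section 9.3.2.2 says "SWE does not have a register on abortions", that the Norwegian birth register holds abortions only from GW 12, and that the Finnish abortion register holds over 99% of terminations found in hospital records.
- **Existing remedy.** Section 9.9 changes the denominator for the Swedish gap, but only for major congenital anomalies. It also plans country-specific rates where stillbirths are involved and analyses of terminations by trimester.
- **Outcome list.** The fourth objective 7 outcome is stillbirths in Section 8 and live births in Section 9.7.5. The Abstract names both.

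**The concern.** Anonymous abortion data can enter a national total but cannot be linked to a woman with MS. The same Table 6 denominator therefore covers more in cohort 6 than in cohort 3, for Sweden throughout and for Norway before GW 12. A prevalence taken over the larger base and applied to the smaller cohort 3 total understates the expected count. Matching on country cannot repair a mismatch that lies within country. Removing women with MS from the national figures changes almost nothing: 1671 of about 2.9 million pregnancies is 0.06%.

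Objective 7 is the protocol's only comparison of MS pregnancies unexposed to any disease-modifying drug with women without MS. A ratio produced by the denominator could be read as an effect of MS.

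**Working it through.** **Inputs from the protocol.** Section 9.5 gives 777 (Finland), 482 (Sweden) and 412 (Norway) MS pregnancies, 1671 in all, with 76% unexposed to any MS drug. The stated cohort 3 size reproduces: 0.76 x 1671 = 1269.96, i.e. 1270. By country this is 590.5, 366.3 and 313.1. Table 5 describes the Swedish base as births, so treating it as all events is approximate; this affects the pooling weights, not the within-country ratios.

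**Assumptions.** The only abortion figure in Section 9.5 is 20% for Norway. The text there describes it as excluding terminations, so it cannot serve as a termination share. Assumed instead:
- terminations a = 5-25% of all events;
- a share e = 80-95% of Norwegian terminations before GW 12;
- spontaneous abortion 10% and ectopic pregnancy 1.5% of events;
- stillbirth 0.4% of births.

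True outcome shares are set equal in the two cohorts.

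**Formulas, observed/expected (O/E) by country.** Let h be the hidden share of events: 0 in Finland, a in Sweden, a x e in Norway. Let b be births as a share of events.
- Spontaneous abortion and ectopic pregnancy: O/E = 1/(1-h).
- Live birth and stillbirth: O/E = (a+b)/(a-h+b).

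**Worked case, a = 15%, e = 90%.** b = 1 - 0.15 - 0.10 - 0.015 = 0.735.
- *Spontaneous abortion.* Sweden 1/0.85 = 1.18; Norway 1/0.865 = 1.16; Finland 1. Observed: 590.5 x 0.10 + 366.3 x 0.10/0.85 + 313.1 x 0.10/0.865 = 59.1 + 43.1 + 36.2 = 138.3. Expected: 127.0. Pooled O/E = 1.09, approximate Poisson 95% CI 0.92-1.29.
- *Live birth.* Sweden 0.885/0.735 = 1.20; Norway 0.885/0.750 = 1.18; Finland 1. Pooled 1012.8/918.9 = 1.10, CI 1.04-1.17.
- *Ectopic pregnancy.* Pooled 1.09, CI 0.71-1.68. *Stillbirth.* Pooled 1.10, CI 0.42-2.91.

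**Range, a = 5-25%, e = 80-95%.**

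| O/E, no true difference | Sweden | Norway | Finland | Pooled |
|---|---|---|---|---|
| Spontaneous abortion, ectopic | 1.05-1.33 | 1.04-1.31 | 1.00 | 1.03-1.17 |
| Live birth, stillbirth | 1.06-1.39 | 1.05-1.37 | 1.00 | 1.03-1.20 |

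Read as expected/observed, the pooled values are 0.85-0.98 and 0.83-0.97.

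**Chance of a false signal.** This is the probability that an exact Poisson 95% CI for O/E lies wholly above 1 with no true difference (about 2% nominal; 1% for Swedish ectopic counts). Here prevalence is taken in cohort 3 as observed, and where Norway is affected all its terminations are treated as hidden.
- Spontaneous abortion at 10%, a = 20%: 26% in Sweden; 22% pooled with both countries affected; 9% pooled with Sweden only. At 5% prevalence the pooled figure with both affected falls to 13%.
- Swedish live births: 98% if hidden terminations are 20% of terminations plus births, 50% at 10%.
- Ectopic pregnancy at 1.5%: 3-8% pooled for a = 10-25%.

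**Norwegian register start.** Section 9.3.1.2 dates the Norwegian Patient Register to 2008; the Norwegian study period starts in 2004, so 7 of 11 years are covered. Against a complete benchmark, with a = 15% and e = 90%, the visible base per true event is (4 x 0.750 + 7 x 0.865)/11 = 0.823, and O/E for spontaneous abortion is (7/11)/0.823 = 0.77. Over a = 5-20% it is 0.70-0.82, i.e. the opposite direction.

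**Benchmark without terminations.** If cohort 6 drops terminations while cohort 3 keeps them under Table 6, Finland becomes misaligned: O/E is 1-a for spontaneous abortion (0.85 at a = 15%) and b/(a+b) for live birth (0.735/0.885 = 0.83).

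**After alignment.** With denominators limited on both sides to what cohort 3 can see, O/E is 1.00 in every country.

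**The case against.** The strongest reply is that the error depends on a choice not yet made. Section 9.7.5 speaks only of relevant official statistics, Section 8 adds a proviso about availability by country, and neither says that induced abortions enter the cohort 6 denominator. Table 2 lists Swedish terminations as not recorded. A separate statistical analysis plan is promised, and choosing rows of national tables could belong there. This makes the bias conditional, and that stands. It does not remove the point: Table 6 is a stated rule for every study cohort, and either uniform choice on the cohort 6 side misaligns at least one country.

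A reader might infer that the ratios will exceed 1 and that the study will report an excess of these outcomes in women with MS. The documents do not support that:
- Section 9.7.5 puts expected before observed, and that ratio would fall below 1.
- Finland is unaffected under Table 6, which dilutes the pooled figure.
- The 2008 register start can reverse the direction for Norwegian spontaneous abortion and ectopic pregnancy.
- For ectopic pregnancy the shift is small against its precision.

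The largest false-signal figure concerns live births, which Section 8 does not list under objective 7, and an excess of live births is hardly an adverse signal. Malformations in live or still births escape the problem if births are the denominator.

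**Conclusion.** The concern holds in conditional form. Under the Table 6 denominators, cohort 3 and a benchmark that counts all terminations are not comparable in Sweden or Norway, and nothing in the protocol aligns them for objective 7. Stillbirth shares the live-birth denominator and the same problem, though expected counts of about four leave its ratio very imprecise. The sizes rest on an assumed termination share of 5-25% and on the chosen statistics including those terminations: O/E of 1.05-1.33 in Sweden for spontaneous abortion and ectopic pregnancy, about 1.03-1.17 pooled before any effect of the Norwegian register start, and up to 1.39 in Sweden for live birth. The sign of the reported departure depends on which way the ratio is formed. Objective 7 is exploratory, so this should be corrected but does not threaten the study's main conclusions.

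**What to change.** In Section 9.7.5:
1. State that the cohort 6 numerator and denominator in each country are restricted to the event types, gestational ages and calendar years observable in cohort 3: no terminations in Sweden, only those from GW 12 in Norway, all in Finland, and Norwegian spontaneous abortions and ectopic pregnancies from 2008, with cohort 3 cut to the same years for those two outcomes.
2. Where the official tables cannot be split this way, remove terminations from both cohorts. With births alone as denominator, live birth becomes the complement of stillbirth and its ratio carries little information, so the split tables are preferable.
3. Define the ratio as observed/expected.
4. Reconcile the objective 7 outcome list across the Abstract, Section 8 and Section 9.7.5.

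The cost is a few sentences and different rows of the same national tables. The downside is that these ratios are no longer interchangeable with the Table 6 prevalences reported under the other objectives, which a table footnote can say.

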Analyses of congenital malformations, ectopic pregnancies, spontaneous abortions, live births and stillbirths in the general population of women without MS in FIN, SWE and NOR will be based on relevant official birth health statistics available from these countries. The expected numbers of these outcomes in each study cohort will be estimated based on the age-matched population prevalence in each country and compared with the observed number of events using standardized prevalence ratios with 95% CIs.

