### **Patient Registers (FIN, SWE, NOR)**

Information on hospitalisations due to MS, spontaneous abortions, and ectopic pregnancies will be obtained from the Patient Registers in this study. The Patient Register includes individual-level inpatient data in FIN SWE and NOR (established: FIN 1969, SWE 1987, NOR 2008). Outpatient visits are available since 1998 in FIN, 2001 in SWE and 2008 in NOR. The registers include data on hospitalisations with information on diagnosis (ICD-10), start and end date of the hospitalisation period, operations and other procedures performed, and identification of the hospital and the hospital district. In addition, outpatient visits in the secondary healthcare units and day surgeries are included the registers. No primary care data are currently available.

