#### Congenital malformations

The Finnish Malformation Register receives data on congenital anomalies from hospitals, healthcare professionals and cytogenetic laboratories. It also draws data from the MBR, the Patient Register for Health Care (including Information on Outpatient Services in Specialized Health Care), the Register on Induced Abortions, and the Register of Visual Impairment, all maintained by THL, as well as from the data provided by the National Supervisory Authority for Welfare and Health (Valvira), and from the Causes of Death Register, maintained by SF. The diagnoses obtained from these data sources are confirmed by contacting the hospitals that have given treatment to the infant/foetus. Although the Register mainly collects data from the first year of the infant for monitoring, it also collects data on subsequently detected congenital anomalies for statistics and research. Data check-ups are made regularly, missing cases and case-specific data are added from the MBR, for instance, and any unclear cases and diagnoses are checked and ascertained by contacting the treating hospitals.

The data content and the data collection practices of the Malformation Register were revised in 1985, 1993 and 2005. From 1993 onwards the data coverage can be regarded as very good although there have been no coverage analyses since the 1993 revision. The prevalence of cases with congenital anomalies corresponds to the normal prevalence described in the literature and reported internationally. The prevalence rates of different types of congenital anomalies have also been consistent with the findings of other national and international studies on congenital anomalies. Since 2005, data on congenital malformations have also been derived from the statistics on information on Outpatient Services in Specialized Health Care, which has further improved the total coverage of the Malformation Register to some extent.

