## 9.5 Study size

Based on the feasibility study (cf. Annex 1) it is estimated that a total of 1671 MS pregnancies would be available for the current study from FIN, SWE and NOR. This total sample size was estimated as follows: In FIN 433 MS pregnancies were observed between 1 January 1996 and 31 December 2010 of which 86 were in 2010. For the actual study, data from FIN from 1 January 2011 to 31 December 2014 will also be used, and therefore the total number of available MS pregnancies was estimated to be 777 (433 + 4\*86, where 86 is the number of MS pregnancies in 2010). In SWE 329 MS pregnancies were observed during the time period 1 July 2005 – 31 December 2011 (329/6.5 years = 51 per year). Because the study period in SWE is from 1 January 2005 to 31 December 2014, the estimated number of MS pregnancies in SWE is 482 (329 + 3\*51). In NOR, 330 MS births were expected to occur in the time period 1 January 2004 – 31 December 2014, which was estimated to be 80% of all MS pregnancies excluding terminations of pregnancies. The number of MS pregnancies available in the study from NOR was thus estimated to be 412 (330/0.8). The total number of 1671 MS pregnancies available for the study is obtained as the sum of these estimated numbers (777 + 482 + 412).

From the 433 MS pregnancies in FIN, 102 (24%) and 331 (76%) were identified as exposed and unexposed to any MSDMD, respectively (in SWE, the proportion of unexposed to any MSDMDs was 77%). Furthermore, of the 433 MS pregnancies in FIN, 95 (22%) and 338 (78%) were identified as exposed and unexposed to IFN- $\beta$  regardless of exposure to other MSDMDs, respectively (personal communication with [name], THL, 15 May 2014). Based on these numbers, it was estimated that 76% (= 331/433) of all MS pregnancies will be unexposed to any MSDMD and 78% (= 338/433) of all MS pregnancies will be unexposed to IFN- $\beta$  (regardless of exposure to other MSDMDs). Based on a systematic review of MSDMD usage (La Mantia et al. 2014), it was estimated that 80% of those identified as exposed to IFN- $\beta$  would not be using other MSDMDs (368\*0.8 = 294). Table 5 presents the study population size by exposure to IFN- $\beta$  based on these assumptions.

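### Objective 7 standardises the MS versus general-population comparison on age and country only; with Finnish MS pregnancies projected to cluster in 2010-2014, a time trend in recorded prevalence can shift the ratio from 1 without any MS effect

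*Protocol*

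**What the plan says.** Three places in the protocol describe the comparison of cohort 3 (MS, unexposed to any MSDMD) with women without MS (cohort 6):

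- Section 4 (Abstract, data analysis): expected numbers "will be estimated based on the age-matched population prevalence in each country".
- Section 8, objective 7: "The observed numbers of pregnancy outcomes in cohort 3, matched for age and country, are compared with the expected numbers through indirect standardisation". The null is that cohort 3 has the prevalence of women without MS.
- Section 9.7.5, text after Table 7: "the observed numbers of pregnancy outcomes matched for age and country in cohort 3 will be compared to the numbers calculated for cohort 6". The cohort 6 figures "are to be estimated based on relevant official birth health statistics available from these countries".

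None of the three names calendar year or says which years of official statistics supply the reference prevalences.

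Four other sections bear on time:

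- Section 9.5 gives 433 Finnish MS pregnancies in 1996-2010 and projects 2011-2014 as 4 × 86, "where 86 is the number of MS pregnancies in 2010".
- Section 9.3.1.2 (Patient Registers), the source for spontaneous abortions and ectopic pregnancies: "Outpatient visits are available since 1998 in FIN, 2001 in SWE and 2008 in NOR".
- Section 9.3.2.2 (Congenital malformations) reports that outpatient data were added in Finland from 2005, "which has further improved the total coverage of the Malformation Register to some extent".
- Section 9.7.6 accepts that changes in diagnosis, treatment and obstetric care may affect prevalence, and says in general terms that year will be allowed for. Its one concrete step is a 2005-2014 sensitivity analysis of the primary objective.

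**The concern.** Indirect standardisation gives a ratio of 1 under the null only if the reference prevalences apply to the same mix of strata as the index cohort. Where year is not a stratum and the prevalences are pooled over the period, one of two further conditions is needed: either both populations have the same calendar mix, or recorded prevalence has no net trend across the window. The protocol's Finnish counts do not suggest the first, and its own account of register changes gives no assurance of the second.

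At stake is how the ratio is read. Recording that improves over time would look like an excess of malformations or losses in unexposed MS women, and a falling trend would look like a deficit. Year is a covariate in the log-binomial models of section 9.7.3, but those models do not produce this ratio.

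**Working it through.** **Reproducing the plan's counts (section 9.5).** Finland 433 + 4 × 86 = 777. Sweden 329 + 3 × 51 = 482. Norway 330/0.8 = 412.5, stated as 412. Total 777 + 482 + 412 = 1671. These agree with the protocol. It states no value for the standardised ratio.

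**Calendar mix in Finland.**
- 1996-2009: 433 − 86 = 347 over 14 years, or 24.8 a year.
- 2010-2014: 5 × 86 = 430, and 430/777 = 55%. Those years are 5/19 = 26% of the window.

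**Assumptions not given in the protocol.** General pregnancies are even over 1996-2014. Cohort 3 has the year mix of all MS pregnancies. The yearly split before 2010 is bracketed by two shapes:
- Flat: 24.8 a year to 2009, then 86 a year.
- Geometric: each earlier year is 0.81 times the next, so that 1996-2010 sums to 433 with 86 in 2010; then 86 a year.

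The mean calendar year is 2007.8 (flat) or 2009.1 (geometric) for MS pregnancies, against 2005.0 for the general population.

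**Formula.** With p(y) the recorded prevalence in year y, identical in both populations (no MS effect), and w(y) the MS count:

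observed/expected = [Σ w(y)p(y) / Σ w(y)] ÷ [Σ p(y) / 19]

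For a one-off step by a factor k, this becomes [1 + s_MS(k − 1)] / [1 + s_G(k − 1)], where s_MS and s_G are the shares of pregnancies after the step.

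| Assumed change in recorded prevalence | Flat | Geometric |
|---|---|---|
| −3% a year | 0.92 | 0.88 |
| −1% a year | 0.97 | 0.96 |
| +1% a year | 1.03 | 1.04 |
| +3% a year | 1.08 | 1.12 |
| +10% step in 2005 | 1.02 | 1.03 |
| +30% step in 2005 | 1.05 | 1.09 |
| +30% step in 1998 | 1.01 | 1.02 |

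Worked case, +30% step in 2005, where s_G = 10/19 = 0.526:
- Flat: s_MS = (5 × 24.8 + 430)/777 = 0.713, so the ratio is 1.214/1.158 = 1.05.
- Geometric: s_MS = 0.861, so the ratio is 1.258/1.158 = 1.09.

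Section 9.7.5 describes the ratio as expected to observed, so its values would be the inverses of these.

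**Pooled over countries.** If Sweden and Norway are unbiased (482 + 412 = 894), the pooled ratio at +3% a year is (777 × 1.085 + 894)/1671 = 1.04 (flat) or (777 × 1.122 + 894)/1671 = 1.06 (geometric).

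**Against random error.** Finnish cohort 3 is about 777 × 331/433 = 594.
- At 2.6% (section 9.5, EUROCAT malformations) to 3.7% (section 9.5, serious adverse outcomes among all women, used as an upper stand-in), 15.4 to 22.0 events are expected. The 95% CI factor exp(1.96/√E) is 1.65 to 1.52, which is larger than any bias in the table.
- For hospital-recorded spontaneous abortion at an assumed 10%, E is about 59 and the factor is 1.29. At +3% a year an exact Poisson 95% CI around the ratio would exclude 1 in about 8% (flat) to 13% (geometric) of studies, against 3.7% with no trend.

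**With year strata.** The expected count becomes Σ w(y)p(y), so the ratio is 1.00 under no MS effect for any trend.

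**The case against.** The strongest reply is that the protocol is silent on reference years rather than wrong about them. Section 9.7.6 says year will be allowed for, section 9.7 promises a detailed analysis plan, and the reference period of an exploratory standardisation could be settled there. Part of this stands. A reader might infer that the protocol prescribes prevalences pooled over the whole period; it does not say so, and the bias depends on that choice. But the standardisation variables are not left open. They are named in three places without year, and an analysis plan that follows them would omit it. The general sentence in section 9.7.6 supplies no year-specific expected counts.

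The second reply concerns size, and it largely stands. The protocol gives no trend magnitude. A steady +3% a year for 18 years is a cumulative rise of 70% (1.03^18 = 1.70), which nothing in the document supports. The Finnish change it does document for hospital-recorded losses, in 1998, moves the ratio by only 1-2% even at an assumed 30% step, because few pregnancies precede it. For malformations, section 9.3.2.2 regards coverage as already very good from 1993, so a 30% step in 2005 is generous.

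Third, most of the late clustering is itself a projection: 344 of the 430 late pregnancies (4 × 86) extrapolate one year's count. That qualifies the 55%. The observed figures still show 86 in 2010 against 24.8 a year before.

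**Conclusion.** The point holds in a limited form. As written, the comparison standardises on age and country only, and if pooled prevalences are used the Finnish ratio can depart from 1 with no MS effect. The departure is about 3-4% for a trend of 1% a year and 8-12% for 3% a year, and 2-9% for a 10-30% recording step in 2005. Every trend and step size is an assumption, as are the even spread of general pregnancies and cohort 3's year mix.

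Three wider readings are not supported:

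- That the bias affects all three countries. Late clustering is shown only for Finland (777 of 1671). Sweden is projected at a constant 51 a year and Norway has no yearly split.
- That any trend produces bias. A non-monotone trend can cancel, and a country whose two populations share a calendar mix is unbiased.
- That the answer to the CHMP request is compromised. Sections 7 and 8 put that request in terms of outcomes in MS women unexposed to IFN-β. The comparison with women without MS is an exploratory addition.

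This is a correction worth making to an exploratory analysis, and it does not touch the primary comparisons.

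**What to change.** In the Abstract, section 8 (objective 7) and section 9.7.5, change the strata to country × maternal age × calendar year of outcome. Where annual tables are sparse or unavailable, use multi-year periods, split in Finland at 2005 and 1998. State the reference years of the official statistics, and obtain the expected numbers by applying the stratum prevalences to cohort 3's own year distribution.

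No further patient data are needed. The cost is that national statistics must be requested by year or period. The protocol relies on whatever official statistics exist, so age-by-year tables may not be available for every outcome, and some may come only in broad periods. In that case the report should state the period used and note that a trend within it is not removed.
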